#### 6.24 **Data Safety and Monitoring:**

6.24.1 All adverse events requiring reporting will be submitted to [name] as described above. Adverse events that are *serious AND unexpected AND related* will be forwarded to the study chair and the URCC Data Safety and Monitoring Committee (DSMC) chair immediately upon receipt at URCC. Additional information may be requested upon their review.

6.24.2 All adverse events reported to URCC are entered into a protocol-specific spreadsheet. Adverse event rates are monitored utilizing the spreadsheet. If a serious adverse event is being reported frequently, the study chair will conduct a detailed review. The DSMC chair will be notified and will determine if further action is required.

6.24.3 The URCC Data Safety Monitoring Committee (DSMC) will review study progress and cumulative reports of adverse events at annual meetings. An overall assessment of accrual and adverse events will enable the committee members to assess whether significant benefits or risks are occurring that would warrant study closure.

6.24.4 The URCC will notify the NCORPs immediately of any serious safety concerns identified by the DSMC. DSMC reports will be available for download on the Research Base website.

---

### 7.0 Patient Reported and Functional Measures

---

7.1 The **On Study Data/Participant Record** and **Clinical Record Information** forms are used to record demographic and clinical information. Diagnostic, treatment and other clinical information will be abstracted from the participant's chart and recorded on these forms. These data will be used for descriptive purposes, to aid in participant monitoring, for moderator analyses and for exploratory analyses.

7.2 The two **Medication and CAM Usage** forms will track the participant's use of prescription and non-prescription sleep and stimulant medication, as well as any other sleep and stimulant aids used during each assessment conducted during the study. These forms will also specifically ask participants to report the use of any CAM modalities for any reason.

#### 7.3 **Insomnia and Sleep Assessments:**

7.3.1 **Insomnia** will be measured by the **Insomnia Severity Index (ISI)**, which is a well-validated self-report measure of insomnia. The measure consists of seven questions on a 5-point Likert Scale with a total score ranging from 0-28. Reliability and validity of this measure have been established. Total score will be used.

7.3.2 **Sleep quality** will be assessed by the **Pittsburgh Sleep Quality Inventory (PSQI)**, a commonly used, 24-item psychometrically sound measure scored for both global severity and subscale scores. The PSQI will assess sleep initiation and maintenance problems and possible etiologic factors (e.g., pain,

nightmares, and hot flashes). Total score will be used. This measure takes less than 5 minutes to complete.

7.3.3 **Number of hours of sleep and intended sleep period** will be calculated from the Daily Diary. For each day of the study period when sleep is assessed, participants will indicate time to bed at night and time arose in the morning.

7.3.4 **Sleep Chronotype** will be measured by the Morningness-Eveningness Questionnaire Self-Assessment (MEQ-SA). This is a 19-item self-report instrument that characterizes the sleep chronotype of an individual.

7.4 **Objective Insomnia Symptoms** will be measured via actigraphy. Participants will have their sleep-wake exposure monitored through the use of a wrist-worn actigraphy-based data logger, the Actigraph GT3X manufactured by ActiGraph LLC, Pensacola, FL. The Actigraph GT3X features a variable epoch length that can be set, and has 16MB of non-volatile memory. “Non-volatile” means that even if the battery, which can log 21 days of runtime before needing to be recharged, becomes exhausted, the data remain intact. The motion data will be analyzed using the ActiLife Analysis Software. The program uses a validated sleep algorithm to provide an assessment of sleep by delineating the “in bed” and “out of bed” portions of the day. The software and algorithms calculate the percent of sleep during these two portions of the day. The actigraphy, in conjunction with the sleep/wake diaries, can be used to approximate the timing of both daytime and nighttime sleep. While daily sleep diaries are a common method used to examine patterns of sleep and wakefulness, we will internally validate the at-home monitoring by comparing actigraphy data collected during baseline and follow-up to the daily questionnaires. This measurement strategy allows for an assessment of sleep problems (sleep latency, WASO, sleep efficiency, daytime sleep) which is free from either subjective or observer bias and requires minimal subject compliance, allows for the detection of periods of wakefulness as brief as 30 seconds in duration.

7.5 **Circadian Activity Rhythm** will be assessed using actigraphy. The exact actigraphs used to objectively assess sleep described in section 7.4 will be used. A two-oscillator cosinor model (12 and 24 hours) will be calculated using nonlinear regression methods on the log (activity counts). This model was found to fit the data for cancer survivors (Study 3) better than a single-oscillator model. Mesor (overall), Amplitude, and Acrophase for the 12- and 24-hour cycles will be calculated.

7.6 **Cardiopulmonary Function** (aerobic capacity) will be assessed using the 6-Minute Walk Test, which is a sub-maximal measurement using a 6-minute walk protocol. A recent systematic review has concluded that this method possesses excellent measurement properties, was better tolerated, and was more reflective of activities of daily living than any other walk test in use. Participants are directed to a specific area designated for walking. Participants walk for a total of 6-minutes and cover as much distance as they can during this time. The walk test is optimally performed in a flat, well lit area that allows for a minimum of 100 feet of walking before the participant needs to make a turning motion. For example, the test may be conducted in a hallway (walking back and forth) or a larger room that allows for a circular/square walking pattern. Upon completion of the test, the total distance walked (in feet), exercise heart rate (in beats per minute), and exercise rate of perceived exertion (using the ACSM revised rating of exertion scale) are recorded. This test was easy to implement, and well received in a busy clinical setting in the pilot study of the proposed exercise intervention. The total distance walked in six minutes can be used to estimate gross VO2 (oxygen consumption). Gross VO2 = Resting VO2 + Exercise (or net) VO2. The formula used to estimate gross VO2 is

$$\text{VO}_2 (\text{mL} * \text{kg}^{-1} * \text{min}^{-1}) = [0.1 \text{ mL} * \text{kg}^{-1} * \text{meter}^{-1} * \text{S} (\text{m} * \text{min}^{-1})] + [1.8 \text{ mL} * \text{kg}^{-1} * \text{meter}^{-1} * \text{S} (\text{m} * \text{min}^{-1}) * \text{G}] + 3.5 \text{ mL} * \text{kg}^{-1} * \text{min}^{-1}$$

Where S is speed in meters per minute and G is the percent grade expressed as a fraction.

7.7 **Muscular Function** (strength) will be assessed using The Handgrip Dynamometer Test, which is a grip strength test used to assess the maximal voluntary contraction generated by the arm muscles. The test is administered with the participant standing in anatomical position, the elbow joint angle will be held constant at 180 degrees. Trials

will be performed in an alternating bilateral sequence for a total of six attempts (three with each arm). A fourth test will be performed if any of the values vary by  $\geq 3$  Kg. The average score of the three trials will be used for right and left limbs to calculate static strength. The surgically involved arm(s) for breast cancer participants will be noted for data analysis. This test was also easy to implement and well received in the clinic in the pilot study of the proposed intervention.

- 7.8 Because many symptoms including cancer-related fatigue (CRF), depression, anxiety, mood disruption, cognitive problems and impaired QOL are often present with insomnia, measures of CRF, depression, anxiety, mood, sleep and cognitive problems have been carefully selected to minimize potential confounding and enable assessment of possible confounds between these concepts.
- 7.8.1 **General Symptomatology** will be measured with the Symptom Inventory (SI), a list of 20 symptoms modified from measures created at M.D. Anderson and Memorial Sloan-Kettering Cancer Centers. It is a series of uniscales where the severity of each symptom is indicated by filling in the appropriate circle on an 11-point scale, anchored by 0 = “Not Present” and 10 = “As Bad as You Can Imagine.” An additional eight questions assess the degree that the symptoms interfere with the participant’s quality of life, with 0 = “Did not interfere” and 10 = “Interfered completely.” Ten additional questions assess the degree to which the participant uses specific mind-body techniques to manage symptoms. Medical oncologists at our Cancer Center use this measure as part of clinical care, and we have used it in numerous studies. It will serve as a concurrent self-report measure of symptoms that will be used in exploratory analyses.
- 7.8.2 **Cancer-Related Fatigue (CRF)** will be assessed subjectively via the revised Brief Fatigue Inventory (BFI), which is a 9-item, patient-report instrument with established reliability and validity that we have used in previous studies. The BFI allows for the rapid assessment of fatigue level and its interference with daily activities in cancer patients, and identifies those patients with severe fatigue. The reliability and validity of the BFI were demonstrated in a study of 305 cancer patients and 290 community-dwelling adults. An internal consistency coefficient (Cronbach’s alpha) of 0.96 was demonstrated when the BFI was administered to 305 patients with cancer. This measure was used in the previously mentioned pilot study of the proposed exercise intervention.
- 7.8.3 **CRF** will also be assessed using the Functional Assessment of Chronic Illness Therapy-Fatigue Subscale (FACIT-F). The FACIT-F subscale is a 13 item scale that asks questions directly related to the impact of CRF on daily activities. It was developed by Cella and his group through extensive interviews with oncology professionals and patients experiencing symptoms of cancer, and it has been validated in a series of studies. The basic measure has shown very good test/retest reliability as well as validity. It has become one of the most commonly used measures in oncology, and we have used this scale in our previous studies including the pilot study designed for this protocol.
- 7.8.4 In addition, **CRF** will be assessed subjectively via the Multidimensional Fatigue Symptom Inventory (MFSI). The MFSI is a multidimensional 30-item fatigue scale developed specifically for documenting CRF. In addition to a fatigue total score, the instrument includes subscales for assessing general, physical, emotional, mental and vigor domains of fatigue. The self-report instrument was psychometrically validated among a sample of 304 cancer patients and has been shown to have good fit via confirmatory factor analysis, reliability and validity.
- 7.8.5 **Depressive Symptoms** will be measured with the Center for Epidemiological Studies Depression Scale (CES-D). The CES-D is a 20-item depression scale developed and validated for use with a variety of populations. It is in a format similar to that of the Beck Depression Inventory, but with less emphasis on physical symptoms of depression that may be confounded with disease symptoms or treatment side effects. It has been shown to reliably and validly measure depression in cancer populations, and we have successfully used this measure in previous studies.
- 7.8.6 **Anxiety** will be measured using the Spielberger State/Trait Anxiety Inventory (STAI). In order to reduce the overall patient burden, we will use only the state portion of the questionnaire. This one-page, self-

administered questionnaire consists of 20 short statements which people may use to describe their feelings. Participants are asked to indicate the degree to which they generally experience each particular feeling, ranging from 1 = “Not at all” to 4 = “Very much so” at that time. It is one of the most widely-used assessments of anxiety. Internal consistency coefficients > 0.90 have been shown, along with test/retest reliability coefficients > 0.70. Concurrent, construct, convergent and divergent validity have also been demonstrated. We have successfully implemented this measure in previous studies.

- 7.8.7 **General Mood** will be assessed using the short form of the Profile of Mood States (POMS). The POMS consists of 30 adjectives in 6 subscales (e.g., anxiety, depression), which subjects rate on a five-point scale with “1” = “Not at all” and “5” = “Extremely” to describe their moods over the past week. The POMS has been used extensively in research with cancer patients and has demonstrated reliability and validity.
- 7.8.8 **Cognitive Problems** will be assessed using the Functional Assessment of Chronic Illness Therapy-Cognitive Well-being Subscale (FACIT-Cog). The FACIT-Cog subscale is a 50-item scale that asks questions directly related to cognition. It was developed by Cella and his group through extensive interviews with oncology professionals and patients experiencing symptoms of cancer, and it has been validated in a series of studies. The basic measure has shown very good test/retest reliability as well as validity. It has become one of the most commonly used measures in oncology, and we have used this instrument in our previous studies (e.g., the pilot study designed for this protocol).
- 7.8.9 **Quality of Life (QOL)** will be assessed subjectively via the Functional Assessment of Chronic Illness Therapy (FACIT; FACT-F). The FACIT; FACT-F is a 27-item QOL scale developed specifically for use in cancer clinical trials. It was developed by Cella and his group through extensive interviews with oncology professionals and patients experiencing symptoms of cancer, and it has been validated in a series of studies of 542 cancer patients. The basic measure has shown very good test/retest reliability as well as validity. Along with a total score representing QOL, there are psychometrically validated subscales of physical, functional, social, and cognitive-emotional status. It is one of the most commonly used measures in oncology, and we have used this instrument in our previous studies, including the pilot study designed for this protocol.
- 7.8.10 **Pain** will be assessed via the Brief Pain Inventory (BPI) and the Visual Analog Scale (VAS) to evaluate the severity and quality of pain experienced. The Brief Pain Inventory (BPI) has become one of the most widely used measurement tools for assessing clinical pain. The BPI allows patients to rate the severity of their pain and the degree to which their pain interferes with common dimensions of feeling and function. Initially developed to assess pain related to cancer, the BPI has been shown to be an appropriate measure for pain caused by a wide range of clinical conditions. The BPI has been used in hundreds of studies. In some ways, the BPI is a “legacy” instrument—a self-report measure that has, over time, become a standard for the assessment of pain and its impact. The Visual Analog Scale (VAS) is a measurement instrument that measures joint pain across a continuum of pictures of faces with values from 0 (no pain) to 10 (pain as bad as you can imagine). The question associated with the VAS reads as follows: “Please score the intensity of the pain you feel in your peripheral joints (knee, wrist, fingers/toes, elbow, shoulder, etc.), excluding spine/back pain and pain at the operated area.”
- 7.9 **Physical Exercise/Activity** will be assessed subjectively using the Godin Leisure Time Exercise Questionnaire and a Daily Diary.
- 7.9.1 The amount of leisure time spent in physical activity will be assessed using the Godin Leisure Time Exercise Questionnaire (Godin). The Godin consists of two questions designed to assess the frequency within a typical 7 day week of mild, moderate, and strenuous exercise performed for a duration of at least 15 minutes during a participant’s free time. The measure is easily administered and brief, with a retest coefficient of .62, a concurrent coefficient of .32 and an objective validity coefficient of .56 compared with CALTRAC accelerometry, estimated VO2 max and body composition (via hydrostatic weight). The Godin has also been used successfully in populations of adult cancer patients.

- 7.9.2 The Daily Diary is designed to track compliance and participation in the exercise intervention and additional daily activities. The participant will be asked to take 1-2 minutes and complete the journal each morning upon waking and each evening immediately prior to sleeping. This daily diary was used in the piloted version of the proposed study, and participants completed the forms without any problems.
- 7.9.3 As an objective measure of physical activity, a GT3X+ actigraph will be worn around the waist. The GT3X+ actigraph provides calculated energy expenditure values for Active Energy Expenditure (AEE) in kilocalories and total energy expenditure in Metabolic Equivalents per Time (METs) in kilocalories/min/kg. The GT3X+ actigraph features a variable sample rate which can be set between non-volatile memory. “Non-volatile” means that even if the battery, which can log 31 days of data, becomes exhausted, the data remain intact. The GT3X+ actigraph AEE Algorithm is based on validation studies, copies of which are available upon request. Software supplied by the manufacturer will be used to determine bouts of activity during each assessment period.
- 7.10 **Participant Feedback** regarding their views on the experimental treatment they received will be assessed via completion of a feedback questionnaire by all participants and open-ended qualitative interviews at the conclusion of the study. The information in the feedback questionnaire and interviews will allow us, for future studies, to obtain information needed to alter aspects of the interventions with which participants were displeased and to determine participants’ reactions to the intervention.

---

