**Circadian Rhythms: Results (N = 410)**

**Circadian Rhythms: Results (N = 410)**

intervention not only significantly improved SQI and secondarily, insomnia, wake after sleep onset, and sleep efficiency, but the yoga participants decreased their sleep medication use during the intervention, while the control participants increased sleep medication use.

Multi-oscillator modeling revealed a 12-hour, ultradian rhythm model fit the circadian activity rhythms better than a single-oscillator, 24-hour model and demonstrated significant rhythm differences between groups post-intervention ( $p < 0.05$ ) with a delayed 12-hour acrophase in the yoga group ( $p < 0.05$ ). The yoga group demonstrated higher physical activity during the morning (first 12 hours of the day) and stabilized physical activity throughout the afternoon and evening (second 12 hours of the day); whereas, the standard care control group showed a lower physical activity pattern in the morning and a higher peak in physical activity in the afternoon and evening. Blunted morning circadian rhythms (low physical activity) and excessive peaks (high physical activity) in circadian rhythms during the afternoon and evening are associated with SQI.

Adherence and Adverse Events: Survivors assigned to the yoga arm attended an average of 6.5 of the 8 prescribed sessions for a total of 480 minutes of the prescribed 600 minutes during the 4-week intervention period. Survivors in the yoga arm also reported extra yoga practice outside of the two required yoga sessions, resulting in a total average of 182 minutes each week over 3 days with a rating of perceived exertion of 3.4 (moderate intensity). Contamination in the control condition was very low; 7 participants reported an average of 20 minutes of yoga one time each week with a rating of perceived exertion of 1.0 (very weak) during the intervention period. There were no study-related adverse events. Survivors liked the yoga intervention; 100% found it useful for improving their sleep and would recommend it to other cancer survivors.

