approximately 35 minutes to complete and participants are asked to complete them as close to the end of the baseline week as possible. Treatment notes including all cancer-related treatment should be submitted with this assessment. A 6 minute walk and handgrip test will be conducted to measure strength, and a fasting (minimum of 8 hours) blood draw of approximately 3 tablespoons, will be completed to assess inflammation. Coordinators will call participants to remind them to wear the actigraphs and complete study assessments on the Thursday or Friday prior to the start of the baseline assessment. At the end of the baseline week, a second call is made to remind participants to complete study assessments and to inform them of their study randomization assignment. Alternatively, these reminders can be made in person at the baseline assessment visit. Study coordinators are to inform participants of their study randomization after fitness testing, fasting blood draw and case report forms have been completed. Only NCORP site staff who have completed the URCC Research Base training on functional assessment and blood draw and processing are allowed to perform these assessments and process the blood specimens.

- 6.16 **Intervention:** Participants will begin the intervention immediately after baseline assessments are complete. Participant adherence will be monitored by attendance records, daily diaries, and actigraphy.
- 6.16.1 Participants in the YOCAS® and health education groups will partake in the intervention twice a week for 75 minutes over a 4 week period (study days 0-27 or study weeks 2-5).
- 6.16.2 Participants in the CBT-I group will complete one session a week for 90 minutes over an 8 week period (study days 0-55 or study weeks 2-9).
- 6.17 **Mid-Point Assessment:** Half-way through the intervention, participants will again complete study questionnaires (as detailed in section 6.13 above) as well as the 6 minute walk and handgrip tests, fasting blood draw, 7 more consecutive days of wearing the actigraphs, and continue recording in their daily diaries. The coordinator will call and remind the participants to wear their actigraphs for 7 consecutive days, to continue filling out their daily diaries, and to complete all study assessments.
- 6.17.1 For participants in the YOCAS® and health education groups, the mid-point assessment will be done during study days 7-13 or study week 3.

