- 6.17.2 For participants in the CBT-I group, the mid-point assessment will be done during study days 21-27 or study week 5.
- 6.18 **Post-Intervention:** At the end of the intervention period, participants will complete all study procedures as outlined above and stop entering data in their daily diaries after this assessment. The coordinator will call participants and remind them to wear the actigraphs, complete forms and diaries, and to complete all study assessments.
- 6.18.1 For participants in the YOCAS® and health education groups, the post assessment will be done during study days 21-27 or study week 5.
- 6.18.2 For participants in the CBT-I group, the post assessment will be done during study days 49-55 or study week 9.
- 6.19 **3-Month Post Intervention Follow Up:** At this assessment, participants will again be asked to fill out questionnaires, complete a 6 minute walk and a handgrip test, a fasting blood draw, 7 consecutive days wearing the actigraphs, and filling out daily diaries for that time. The coordinator will complete a scheduling and reminder call during the week prior to the follow-up visit.
- 6.19.1 For participants in the YOCAS® and health education groups, the 3-month post assessment will be done during study week 17.
- 6.19.2 For participants in the CBT-I group, the 3-month post assessment will be done during study week 21.
- 6.20 **6-Month Post Intervention Follow Up:** At this assessment, participants will again be asked to fill out questionnaires, complete a 6 minute walk, and a handgrip test, a fasting blood draw, 7 consecutive days wearing the actigraphs, and filling out daily diaries for that time. Additionally, participants will complete a feedback form

and a 15-minute qualitative exit interview at the end of the 6-month post-intervention assessment period. All participants will be debriefed and the 3 study arms will be explained. The coordinator completes a scheduling and reminder call during the week prior to the follow-up visit.

6.20.1 For participants in the YOCAS® and health education groups, the 6-month post assessment will be given during study week 29.

6.20.2 For participants in the CBT-I group, the 6-month post assessment will be given during study week 33.

6.21 **Management of actigraphy:** Actigraphy will be handled by the PEAK Laboratory at the Research Base.

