- 10.7.4 **Exploratory Mechanistic Aim 4 Analyses:** To explore whether YOCAS® is effective for improving **circadian activity rhythms (24 and 12 hour amplitudes and acrophases via actigraphy), physical function (i.e., cardiopulmonary [6-min. walk] and muscular function [dynamometry]), and inflammation (IL-6, IL-8, IL-10, IL-1 $\beta$ , IFN- $\gamma$ , & TNFR1 via standardized ELISAs and multiplexes)** compared to CBT-I and a health education control, we will use the same analytical methods as for Primary Aim 1 to assess changes in the estimated parameters of the two-oscillator (12 and 24 hours) cosinor model and the Hill function model. These parameters include **Mesor (M), Amplitude (A1) and Acrophase (Phi1) for the 24-hour oscillator and Amplitude (A2) and Acrophase (Phi2) for the 12-hour oscillator.** Estimates will be from the log-transformed activity counts using nonlinear regression. Degree of rhythmicity will be assessed with the Fisher-transformed model multiple correlation. We will also fit single-oscillator models (24-hour Mesor, Amplitude, and Acrophase) for comparison with other published studies. The time participants woke up in the morning and fell asleep in the evening will be extracted from weekly diaries. We will apply the same methods as for physical function and inflammation outcomes; inflammatory biomarkers will be log-transformed as needed.
- 10.7.5 **Exploratory Mechanistic Aim 5 Analyses:** To explore **whether changes in physical function, circadian rhythm and inflammation mediate the effect of YOCAS® on insomnia,** we will use separate mediation analyses performed on pre-post ISI change scores (CS) and the above outcomes as potential mediators. Path analysis will be used, where the intervention affects CS, the intervention affects the mediator, and the mediator, in turn, affects the CS. We will also use structural equation modeling. Mediation will be assessed via indirect effect estimation using bootstrap-based 95% confidence intervals. Latent variables will be introduced into the model for multiple measures of a common entity (e.g., cytokines for inflammation). If multiple measures are weakly correlated, we will split them

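### Post-intervention actigraphy is recorded wholly within the last class week, and no rule keeps class time out of the daytime-napping score or separates it in the circadian fits

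*Combined protocol and SAP*

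**What the plan says.** All references are to the combined protocol and SAP.

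- **Classes.** Section 6.16.1 has the YOCAS and health education groups attend "twice a week for 75 minutes over a 4 week period (study days 0-27 or study weeks 2-5"). Section 6.16.2 gives CBT-I "one session a week for 90 minutes over an 8 week period (study days 0-55 or study weeks 2-9").
- **Post-intervention recording.** For YOCAS and health education, Section 6.18.1 states that "the post assessment will be done during study days 21-27 or study week 5". For CBT-I, Section 6.18.2 states that "the post assessment will be done during study days 49-55 or study week 9". Baseline (Section 6.15) is days -7 to -1.
- **Wear.** Section 6.21.3 requires the wrist device day and night for 7 days, with removal only when it would get submerged. Class is not a reason to remove it.
- **Scoring.** On the in-bed and out-of-bed parts of the day, Section 7.4 says "The software and algorithms calculate the percent of sleep during these two portions of the day". For the two-oscillator cosinor model, Section 10.7.4 says "Estimates will be from the log-transformed activity counts using nonlinear regression".
- **Analysis.** Sections 10.7.2 and 10.7.4 apply the primary-aim ANCOVA on the post-treatment value to the actigraphy sleep and rhythm endpoints. Section 10.7.5 then tests rhythm change as a mediator of the YOCAS effect on insomnia.

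**The concern.** Actigraphy infers sleep from lack of movement. YOCAS combines gentle Hatha and Restorative postures with breathing and meditation (Section 6.3), and the other two arms attend classes of a different kind. Some class time may be still enough to be scored as out-of-bed sleep, and some may add activity at a particular clock hour. Both enter the post-intervention value. Adjusting for baseline does not remove them, because the baseline week has no classes.

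Two readings are at stake. A napping difference between arms could partly reflect what happens in class. A shift in the fitted rhythm could partly record attendance at that hour, and Section 10.7.5 would then treat it as a mediator. The second matters because Section 2.0 (Study 1) reports a delayed 12-hour acrophase in the yoga group and takes altered rhythm as a plausible mechanism.

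**Working it through.** **1. Overlap and class minutes** (Sections 6.16 and 6.18)

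| Arm | Class days | Recording days | Overlap | Class min/week | Per day (÷7) |
|---|---|---|---|---|---|
| YOCAS | 0-27 | 21-27 | 7 of 7 | 2 × 75 = 150 | 21.4 |
| Health education | 0-27 | 21-27 | 7 of 7 | 2 × 75 = 150 | 21.4 |
| CBT-I | 0-55 | 49-55 | 7 of 7 | 1 × 90 = 90 | 12.9 |

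Home practice adds to the YOCAS figure. Section 2.0 reports attendance plus extra practice in the prior trial as "resulting in a total average of 182 minutes each week over 3 days", which is 182/7 = 26.0 min/day.

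**2. Sample size.** The plan gives no figure for the actigraphy endpoints. They inherit 168 evaluable per arm from the ISI calculation in Section 10.2.1, which reproduces: SD = 4.6 × √(1 - 0.576²) = 3.760; n = 2 × (1.960 + 0.842)² × 3.760² / 1.15² = 168.

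**3. Napping.** With fraction f of m weekly minutes scored as sleep, false napping is f × m / 7 min/day. From class time alone (m = 150), f = 10%, 25%, 50% and 100% give 2.1, 5.4, 10.7 and 21.4 min/day. The arm difference is (f_Y × m_Y - f_C × m_C) / 7. The documents give no misscoring rate, so each f is an assumption. Here YOCAS has 182 min:

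| Comparison | Assumed f | Difference (min/day) |
|---|---|---|
| Any comparator, none of its class misscored | YOCAS 25-50% | +6.5 to +13.0 |
| Health education (150), equal rates | 25-50% both | 32f/7 = +1.1 to +2.3 |
| Health education (150), seated class misscored more | YOCAS 25%, HE 50% | (45.5 - 75)/7 = -4.2 |
| CBT-I (90), equal rates | 25-50% both | 92f/7 = +3.3 to +6.6 |

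The unadjusted SE of an arm difference is SD × √(2/168): 3.3 min at an assumed SD of 30 min/day and 6.5 at 60. In the one-sided case (only YOCAS classes misscored, 25%, 5.4 min/day), the chance of a significant difference at two-sided 0.05 with no true effect is 70% at SD 20 and 13% at SD 60.

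**4. Circadian fits.** The model is y(t) = M + A1·cos(2π(t - φ1)/24) + A2·cos(2π(t - φ2)/12), fitted by least squares to 7 simulated days of 1-minute epochs. Two 75-minute sessions change log activity by 1-2 units. Assumptions: A1 = 1.5, A2 = 0.3-0.5 log units, 24-hour peak at 15:00, 12-hour peak at 08:00-12:00 or 15:00.

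- Classes at 09:00, 10:00, 13:00 or 18:00 move the 12-hour acrophase by about 1-22 min and the 24-hour acrophase by about 2-9 min.
- The sign depends on class hour and underlying phase. With A2 = 0.3, a 12-hour peak at 10:00 and a 2-unit rise, a 13:00 class gives +22 min and an 18:00 class -22 min. With the peak at 15:00 the same classes give -13 and +22.
- Averaged over start times from 09:00 to 19:00, the 12-hour shift is at most about 3 min in every scenario run.

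**5. Cost of masking.** 150/10,080 = 1.5% of recorded minutes for YOCAS and health education; 90/10,080 = 0.9% for CBT-I.

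**The case against.** A reader might infer that YOCAS will be credited with extra naps. The documents do not support a direction. Health education is matched on class minutes and describes no exercise content, so at equal misscoring little remains and the sign can reverse. Section 2.0 also rates yoga in the prior trial as moderate exertion, which argues against mostly motionless sessions.

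A reader might also infer that naps have no self-report check. Section 7.3.3 names only bed and rising times, but the diary form is not in the documents. Section 7.4 uses diaries alongside actigraphy to approximate daytime as well as night-time sleep, and Section 7.9.2 says the diary covers daily activities. What stands is that comparing the two sources is not a rule for excluding class time.

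On rhythm, no class hour is fixed and Section 6.6.2 leaves logistics to sites, over roughly 720/30 = 24 to 720/15 = 48 cohorts. Unless class hour differs systematically by arm, much of the shift is noise. Activity during yoga is also arguably part of the effect, since Section 2.0 theorises that exercise entrains the clock. Making a masked fit the main analysis would change the estimand and weaken comparability with the prior trial. That argument stands for the circadian endpoints. It does not stand for napping: a participant in class is awake, and scoring that time as sleep is error under any estimand.

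**Conclusion.** The concern holds as a gap in scoring and interpretation. The complete overlap, the class-free baseline and the absence of any separating rule are plain in the text. Class content differs between arms, and scheduled minutes differ against CBT-I (150 versus 90 per week).

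The size is uncertain. False napping cannot exceed 21.4 min/day from YOCAS classes, or 26.0 with practice at the prior-trial level, and the net arm difference may be near zero or of either sign. The acrophase shift is a matter of minutes. These figures rest on assumed misscoring rates, nap SDs, amplitudes, phases and class hours, none of which the documents give.

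It would go too far to say that the mechanistic aim cannot tell attendance from rhythm change. The supported statement is that the planned analyses do not check this. The primary ISI, the PSQI and in-bed measures (latency, efficiency, wake after sleep onset) are untouched by this route. The exposed items are one secondary endpoint and the exploratory circadian outcomes and mediator.

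**What to change.** 1. **Section 6.9:** add class start and end times to the existing attendance log.
2. **Sections 7.4 and 10.7.2:** exclude attended class intervals from daytime-sleep scoring in all three arms, and report the unmasked result as a sensitivity analysis.
3. **Sections 7.5, 10.7.4 and 10.7.5:** keep the all-activity cosinor fit as the main analysis. Pre-specify a repeat with class intervals masked, or on non-class days only, and require agreement before a rhythm change is read as a mechanism or mediator.
4. Report the 3-month actigraphy, when no classes run, as supporting evidence. It is not free of yoga: Section 9.2 supplies kits to sustain home practice through the following 6 months.

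The cost is one logged field, modest extra processing and about 1-1.5% of recorded minutes. Home practice is left unmasked, because the documents do not show that its clock times are recorded.
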